**Table 2: Schedule of Events – Follow-up Period**

| Study Procedures                                | Follow-Up Period |       |      |                  | ET Visit
(if applicable) |
|---|------------------|-------|------|------------------|-----------------------------|
|   | V15              | V16   | V17  | EOS Visit
V18 |                             |
| In-Clinic Visit (V)                      |                  |       |      |                  |                             |
| Week (Wk)                                       | Wk16             | Wk20  | Wk24 | Wk28             |                             |
| Day (D)   | D113             | D141  | D169 | D197             |                             |
| Visit Window in days (d)                        | ±3 d             | ±3 d  | ±3 d | ±3 d             |                             |
| Treatment:                               |                  |       |      |                  |                             |
| Concomitant medications/procedures              | X                | X     | X    | X                | X                           |
| Efficacy:                                |                  |       |      |                  |                             |
| SDI/EEsAI (PRO)                   | X                | X     | X    | X                | X                           |
| EoE-QOL-A (PRO)                   | X                | X     | X    | X                | X                           |
| EoE-EREFs                           |                  |       |      |                  | X                           |
| Safety:                                  |                  |       |      |                  |                             |
| Weight  | X                | X     | X    | X                | X                           |
| Diet History                                    | X                | X     | X    | X                | X                           |
| Physical examination; ECG                       |                  |       |      | X                | X                           |
| Adverse events                                  | X                | X     | X    | X                | X                           |
| Laboratory Testing:                      |                  |       |      |                  |                             |
| Hematology and serum chemistry                  | X                | X     | X    | X                | X                           |
| Coagulation                                     |                  |       |      |                  | X                           |
| Urinalysis                                      | X                | X     | X    | X                | X                           |
| Pregnancy testing                               |                  | Urine |      | Serum            | Serum                       |
| Endoscopy with esophageal biopsies  |                  |       |      |                  | X                           |
| Research samples (serum/plasma)                 |                  | X     |      | X                |                             |
| PK and ADA Testing:                      |                  |       |      |                  |                             |
| PK sample                                       | X                | X     | X    | X                | X                           |
| ADA sample                          |                  |       |      | X    | X               |

ADA = anti-drug antibody; ECG = electrocardiogram; EEsAI = Eosinophilic Esophagitis Activity Index; EoE-EREFS = Eosinophilic Esophagitis-Endoscopic Reference Score; EoE-QOL-A = Adult Eosinophilic Esophagitis Quality of Life (questionnaire); EOS = end of study; ET = early termination; PK = pharmacokinetic; PRO = patient-reported outcome; SDI = Straumann Dysphagia Instrument.

 Questionnaires will be completed before any other assessments or procedures.

 The SDI/EEsAI PROs should be done by the patient electronically, weekly for SDI, and daily and weekly for EEsAI from the beginning of screening through EOS or ET. Site should confirm patient compliance at each clinic visit.

 The EoE-QOL-A PRO should be recorded at baseline and then monthly through EOS or ET.

 EoE-EREFS should be completed when endoscopy with esophageal biopsies procedure is performed.

 The EndoFLIP procedure, with photographs, to measure esophageal distensibility will be performed during the endoscopy procedures.

### 10.3. Criteria for Treatment-Emergent Potentially Clinical Significant Value (PCSV) for Dupilumab studies

| Parameter                 | Treatment Emergent PCSV  | Comments   |
|---------------------------|--|--|
| Clinical Chemistry |  |  |
| ALT*                      | 
>3 and <math>\leq</math> 5 ULN and baseline <math>\leq</math> 3 ULN*
 
>5 and <math>\leq</math> 10 ULN and baseline <math>\leq</math> 5 ULN
 
>10 and <math>\leq</math> 20 ULN and baseline <math>\leq</math> 10 ULN
 
>20 ULN and baseline <math>\leq</math> 20 ULN
 | 
Enzyme activity must be expressed in ULN, not in IU/L.
 
Concept paper on DILI – FDA draft Guidance Oct 2007.
 
Each category is calculated independently.
 
* At least one level is required, multiple levels are optional for phase 2/3 studies. If it is desirable to get the distribution across the different PCSV levels, additional shift table on <math>\leq</math>3, >3 to <math>\leq</math>5, > 5 to <math>\leq</math>10, >10 to <math>\leq</math>20, and > 20 category for baseline vs. post baseline may be provided
 |
| AST*                      | 
>3 and <math>\leq</math> 5 ULN and baseline <math>\leq</math> 3 ULN*
 
>5 and <math>\leq</math> 10 ULN and baseline <math>\leq</math> 5 ULN
 
>10 and <math>\leq</math> 20 ULN and baseline <math>\leq</math> 10 ULN
 
>20 ULN and baseline <math>\leq</math> 20 ULN
 | 
Enzyme activity must be expressed in ULN, not in IU/L.
 
Concept paper on DILI – FDA draft Guidance Oct 2007.
 
Each category is calculated independently.
 
* At least one level is required, multiple levels are optional for phase 2/3 studies. If it is desirable to get the distribution across the different PCSV levels, additional shift table on <math>\leq</math>3, >3 to <math>\leq</math>5, > 5 to <math>\leq</math>10, >10 to <math>\leq</math>20, and > 20 category for baseline vs. post baseline may be provided
 |
| Alkaline Phosphatase      | >1.5 ULN and baseline $\leq$ 1.5 ULN   | 
Enzyme activity must be expressed in ULN, not in IU/L.
 
Concept paper on DILI – FDA draft Guidance Oct 2007.
  |
| Total Bilirubin*          | 
>1.5 and <math>\leq</math> 2 ULN and baseline <math>\leq</math> 1.5 ULN*
 
>2 ULN and baseline <math>\leq</math> 2.0 ULN
   | 
Must be expressed in ULN, not in <math>\mu</math>mol/L or mg/L. Categories are cumulative.
 
Concept paper on DILI – FDA draft Guidance Oct 2007.
 
* At least one level is required, multiple levels are optional for phase 2/3 studies. If it is desirable to get the distribution of significant level, additional shift table on <math>\leq</math>1.5, >1.5 to <math>\leq</math>2.0 and > 2.0 category for baseline vs. post baseline may be provided
   |
| Conjugated Bilirubin      | (Direct Bilirubin >35% Total Bilirubin and Total Bilirubin >1.5 ULN) and (Direct Bilirubin basis.
<=35% Total Bilirubin or Total Bilirubin
<=1.5 ULN) at baseline  | Conjugated bilirubin dosed on a case-by-case   |

| Parameter               | Treatment Emergent PCSV   | Comments   |
|-------------------------|---|--|
| ALT and Total Bilirubin | (ALT>3 ULN and TBILI>2 ULN) and baseline (ALT <=3 ULN or TBILI <=2 ULN)  | Concept paper on DILI – FDA draft Guidance Oct 2007.   |
| CPK*                    | >3 and $\leq$ 10 ULN and baseline $\leq$ 3ULN*
>10 ULN and baseline $\leq$ 10ULN   | FDA Feb 2005.
Am J Cardiol April 2006.
Categories are cumulative.
* At least one level is required, multiple levels are optional for phase 2/3 studies. If it is desirable to get the distribution of significant level, additional shift table on $\leq$ 3, $>$ 3 to $\leq$ 10, and $>$ 10 category for baseline vs. post baseline may be provided |
| Creatinine              | $\geq$ 150 $\mu$ mol/L (Adults) and baseline < 150 $\mu$ mol/L
$\geq$ =30% change from baseline and <100% change from baseline
$\geq$ 100% change from baseline | Benichou C., 1994.
3 independent criteria   |
| Uric Acid               |   | Harrison- Principles of internal Medicine 17 th Ed., 2008.  |
| Hyperuricemia           | >408 $\mu$ mol/L and $\leq$ =408 $\mu$ mol/L at baseline  |  |
| Hypouricemia            | <120 $\mu$ mol/L and $\geq$ = 120 $\mu$ mol/L at baseline   | Two independent criteria   |
| Blood Urea Nitrogen     | $\geq$ 17 mmol/L and <17 mmol/L at baseline   | Two independent criteria   |
| Chloride                |   | Two independent criteria   |
| Hypochloremia           | <80 mmol/L and baseline $\geq$ 80 mmol/L  |  |
| Hyperchloremia          | >115 mmol/L and baseline $\leq$ 115 mmol/L  |  |
| Sodium                  |   | Two independent criteria   |
| Hyponatremia            | $\leq$ 129 mmol/L and baseline > 129 mmol/L   |  |
| Hypernatremia           | $\geq$ 160 mmol/L and baseline <160 mmol/L  |  |
| Potassium               |   | FDA Feb 2005.  |
| Hypokalemia             | <3 mmol/L and baseline $\geq$ 3 mmol/L  | Two independent criteria   |
| Hyperkalemia            | $\geq$ 5.5 mmol/L and baseline <5.5 mmol/L  |  |
| Total Cholesterol       | $\geq$ 7.74 mmol/L and < 7.74 mmol/L at baseline  | Threshold for therapeutic intervention.  |
| Triglycerides           | $\geq$ 4.6 mmol/L and < 4.6 mmol/L at baseline  | Threshold for therapeutic intervention.  |
| Glucose                 |   |  |
| Hypoglycaemia           | ( $\leq$ 3.9 mmol/L and <LLN) and (>3.9 mmol/L or $\geq$ =LLN) at baseline  | ADA May 2005.  |
| Hyperglycaemia          | $\geq$ 11.1 mmol/L (unfasted); $\geq$ 7 mmol/L (fasted) and < 11.1 mmol/L (unfasted); <7 mmol/L (fasted) at baseline  | ADA Jan 2008.  |
| HbA1c                   | >8% and $\leq$ 8% at baseline   |  |

| Parameter         | Treatment Emergent PCSV   | Comments  |
|-------------------|---|---|
| Albumin           | $\leq 25$ g/L and $> 25$ g/L at baseline  |   |
| CRP               | $> 2$ ULN or $> 10$ mg/L (if ULN not provided) and $\leq 2$ ULN or $\leq 10$ mg/L (if ULN not provided) at baseline   | FDA Sept 2005.  |
| Hematology |   |   |
| WBC               | $< 3.0$ Giga/L and $\geq 3.0$ Giga/L at baseline (Non-Black);
$< 2.0$ Giga/L and $\geq 2.0$ Giga/L at baseline (Black);
$\geq 16.0$ Giga/L and $< 16$ Giga/L at baseline  | Increase in WBC: not relevant.
To be interpreted only if no differential count available.  |
| Lymphocytes       | $> 4.0$ Giga/L and $\leq 4.0$ Giga/L at baseline  |   |
| Neutrophils       | $< 1.5$ Giga/L and $\geq 1.5$ Giga/L at baseline (Non-Black);
$< 1.0$ Giga/L and $\geq 1.0$ Giga/L at baseline (Black)   | International Consensus meeting on drug-induced blood cytopenias, 1991.
FDA criteria.  |
| Monocytes         | $> 0.7$ Giga/L $\leq 0.7$ Giga/L at baseline  |   |
| Basophils         | $> 0.1$ Giga/L $\leq 0.1$ Giga/L at baseline  |   |
| Eosinophils       | $(> 0.5$ Giga/L and $>$ ULN) and ( $\leq 0.5$ Giga/L or $\leq$ ULN at baseline)   | Harrison- Principles of internal Medicine 17 th Ed., 2008.   |
| Hemoglobin        | $\leq 115$ g/L and $> 115$ g/L at baseline for male;
$\leq 95$ g/L and $> 95$ g/L at baseline for Female.

$\geq 185$ g/L and $< 185$ g/L at baseline for Male;
$\geq 165$ g/L and $< 165$ g/L at baseline for Female

Decrease from Baseline $\geq 20$ g/L | Three criteria are independent.

Criteria based upon decrease from baseline are more relevant than based on absolute value. Other categories for decrease from baseline can be used ( $\geq 30$ g/L, $\geq 40$ g/L, $\geq 50$ g/L). |
| Hematocrit        | $\leq 0.37$ v/v and $> 0.37$ v/v at baseline for Male ;
$\leq 0.32$ v/v and $> 0.32$ v/v at baseline for Female
$\geq 0.55$ v/v and $< 0.55$ v/v at baseline for Male ;
$\geq 0.5$ v/v and $< 0.5$ v/v at baseline for Female  | Two Criteria are independent  |
| RBC               | Female
$< 3$ Tera/L and baseline $\geq 3$ Tera/L
$\geq 6$ Tera/L and baseline $< 6$ Tera/L
Male
$< 4$ Tera/L and baseline $\geq 4$ Tera/L
$\geq 7$ Tera/L and baseline $< 7$ Tera/L  | Unless specifically required for particular drug development, the analysis is redundant with that of Hb.
Otherwise, consider FDA criteria.   |
| Platelets         | $< 100$ Giga/L and $\geq 100$ Giga/L at baseline
$\geq 700$ Giga/L and $< 700$ Giga/L at baseline  | International Consensus meeting on drug-induced blood cytopenias, 1991.
Two independent criteria   |

| Parameter                     | Treatment Emergent PCSV   | Comments  |
|-------------------------------|---|---|
| Urinalysis             |   |   |
| pH                            | $\leq 4.6$ and $> 4.6$ at baseline
$\geq 8$ and $< 8$ at baseline  | Two independent criteria  |
| Vital signs            |   |   |
| HR                            | $\leq 50$ bpm and decrease from baseline $\geq 20$ bpm
$\geq 120$ bpm and increase from baseline $\geq 20$ bpm   | To be applied for all positions (including missing) except STANDING.  |
| SBP                           | $\leq 95$ mmHg and decrease from baseline $\geq 20$ mmHg
$\geq 160$ mmHg and increase from baseline $\geq 20$ mmHg   | To be applied for all positions (including missing) except STANDING.  |
| DBP                           | $\leq 45$ mmHg and decrease from baseline $\geq 10$ mmHg
$\geq 110$ mmHg and increase from baseline $\geq 10$ mmHg   | To be applied for all positions (including missing) except STANDING.  |
| Weight                        | $\geq 5\%$ increase from baseline
$\geq 5\%$ decrease from baseline  | FDA Feb 2007.   |
| ECG                    |   |   |
| HR                            | $\leq 50$ bpm and decrease from baseline $\geq 20$ bpm
$\geq 120$ bpm and increase from baseline $\geq 20$ bpm   |   |
| PR                            | $\geq 220$ ms and increase from baseline $\geq 20$ ms   |   |
| QRS                           | $\geq 120$ ms & $< 120$ ms at baseline  |   |
| QTc                           | Absolute values (ms)   | To be applied to any kind of QT correction formula.   |
| Borderline                    | Borderline:   |   |
| Prolonged*                    | 431-450 ms and $< 431$ ms at baseline for Male;
451-470 ms and $< 451$ ms at baseline for Female   |   |
| Additional                    | Prolonged:
$>450$ to $<500$ ms and $\leq 450$ ms at baseline for Male;
$>470$ to $<500$ ms and $\leq 470$ ms at baseline for Female
$\geq 500$ ms and $< 500$ ms at baseline | *QTc prolonged and $\Delta QTc > 60$ ms are the PCSA to be identified in individual subjects/patients listings. |
|                               |   | 5 independent criteria  |
| Increase from baseline |   |   |
| Borderline:                   | Increase from baseline 30-60 ms   |   |
| Prolonged:                    | Increase from baseline $> 60$ ms  |   |

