## **5.8. Analysis of Safety Data**

The summary of safety and tolerance will be performed based on SAF.

The safety analysis will be based on the reported AEs, clinical laboratory evaluations, physical examination, vital signs, and 12-lead ECG.

Thresholds for treatment-emergent Potentially Clinically Significant Values (PCSVs) in laboratory variables, vital signs and ECG are defined in [Appendix 10.3](#). Treatment-emergent PCSV is any PCSV developed or worsened in severity compared to the baseline during the treatment and follow-up period.

The time interval to detect any event or abnormality is between the first injection of study medication and EOS.

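### The asterisked PCSV level for ALT, AST, bilirubin and CPK has an upper limit, so the permitted one-level table can leave out the largest elevations; for bilirubin and CPK the counting comment also contradicts the bands

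*SAP*

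**What the plan says.** SAP Section 5.8 refers to Appendix 10.3 for the PCSV thresholds. Section 5.8.2 plans the number and percentage of subjects with treatment-emergent PCSVs, depending on the data, and does not say which levels are tabulated.

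Appendix 10.3 prints these levels, in multiples of ULN:

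- ALT and AST: above 3 to 5, above 5 to 10, above 10 to 20, above 20.
- Total bilirubin: above 1.5 to 2, above 2.
- CPK: above 3 to 10, above 10.

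Each level requires the baseline to be at or below its lower bound. In all four rows an asterisk stands on the parameter name and on the lowest band. It leads to the rule "At least one level is required, multiple levels are optional for phase 2/3 studies". A shift table across all the categories is left optional.

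The counting comments differ between rows. ALT and AST have "Each category is calculated independently". Total bilirubin and CPK have "Categories are cumulative".

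**The concern.** A required safety count should not fall as the abnormality gets larger. Here the level marked as required is closed at the top, so a table limited to it counts moderate elevations and passes over larger ones. Choosing another single level does not help. Only the highest level is open-ended, and used alone it drops every elevation below it.

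For bilirubin and CPK there is a second problem, which does not depend on how many levels are shown. The comment and the printed bands give different counts, so two programmers following the same appendix could produce different tables.

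For ALT and AST the comment fits the bands. Even with all four lines shown, however, none gives the number of patients above 3 x ULN, and that number cannot be recovered by adding the lines. What is at stake is how the laboratory frequency table reads. No efficacy result is involved.

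**Working it through.** The plan gives no figure to reproduce, so the check applies the printed criteria to test values.

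**Inputs.** The bands are those of Appendix 10.3. Baseline is set at 1.0 x ULN, so every baseline condition is met. Each row is a patient with one elevated reading.

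**Rules.** As printed, a level is met if lower bound < value ≤ upper bound. On the cumulative reading, it is met if value > lower bound. Levels are numbered from the lowest; level 1 carries the asterisk.

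| Parameter | Value (x ULN) | Level met as printed | Levels met, lower bound only | Counted if only level 1 is tabulated as printed |
|---|---|---|---|---|
| ALT/AST | 4 | 1 | 1 | yes |
| ALT/AST | 5 | 1 | 1 | yes |
| ALT/AST | 5.1 | 2 | 1, 2 | no |
| ALT/AST | 12 | 3 | 1, 2, 3 | no |
| ALT/AST | 25 | 4 | 1, 2, 3, 4 | no |
| Bilirubin | 1.8 | 1 | 1 | yes |
| Bilirubin | 2.5 | 2 | 1, 2 | no |
| Bilirubin | 4 | 2 | 1, 2 | no |
| CPK | 5 | 1 | 1 | yes |
| CPK | 10.1 | 2 | 1, 2 | no |
| CPK | 15 | 2 | 1, 2 | no |

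**Results.**

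1. As printed, no single value meets two levels of one parameter. The bilirubin and CPK comment therefore cannot be carried out on the bands beside it.
2. Every value above the upper limit of level 1 is missed by a level-1-only table. With lower bounds only, level 1 catches all of them.
3. The loss is per patient, not per reading. Someone with ALT 12 at one visit and 4 at another has a reading inside the lowest band and is counted. Only a patient whose elevated readings all lie above the band is left out.
4. That same patient meets levels 1 and 3 for ALT when the levels are calculated independently. Adding the four lines would count this patient twice, so the number above 3 x ULN is not their sum.
5. Section 2.2 plans 22 patients per arm, and 1/22 = 0.0455. One omitted patient changes an arm's rate by 4.5 percentage points.

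**The case against.** The best defence is that nothing in the SAP says only one level will be tabulated. All printed levels are PCSV criteria, and Section 5.8.2 does not confine the count to the lowest. The footnote does not name the required level in words; that it is the lowest follows only from where the asterisk stands. This is correct, and it makes the omission conditional on using an option that the appendix allows.

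A reader might infer that a patient going from 1 to 12 x ULN ALT is not a PCSV under this plan. The appendix does not support that, because the value meets the third printed level. The patient is missing only from a table restricted to the lowest band.

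A reader might also infer that large bilirubin and CPK values are certain to be lost. They are not: if the comment is followed in place of the bands, 2.5 x ULN bilirubin and 15 x ULN CPK count at the lower level too. What stands for these two rows is the contradiction.

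Nor would a large value go unseen. Section 5.8.2 provides by-visit descriptive statistics (Section 5 includes the maximum), a count of newly abnormal values, and a listing of all laboratory values with a PCSV flag. Appendix 10.3 has an open-ended combined criterion of ALT above 3 and total bilirubin above 2 x ULN. These reduce the consequence but do not correct the PCSV frequency table.

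Finally, Section 5.8 states "Treatment-emergent PCSV is any PCSV developed or worsened in severity compared to the baseline during the treatment and follow-up period", and it is tempting to say that single-threshold rows such as eosinophils breach it, because a patient already above the threshold cannot be flagged. The documents do not support that as an error. Such a row has no severity grade to worsen through, and the rise would still show in the change from baseline and the listing.

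**Conclusion.** The point holds in a limited form, and it is minor.

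- **All four parameters:** the level marked as required is a closed band, and the footnote permits reporting it alone. If that is done, a patient whose only elevated readings lie above the band is left out of the n (%) table. At the planned size each such patient is worth 4.5 percentage points in an arm. How many there would be cannot be judged from the SAP.
- **Bilirubin and CPK only:** the comment contradicts the printed bands, whichever levels are reported.
- **ALT and AST:** the comment is consistent with the bands, but no line gives the number of patients above 3 x ULN.

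The first conclusion assumes that the asterisk marks the required level and that the one-level option is used. The second needs neither assumption. Safety is summarised descriptively, so no test or error rate is affected.

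**What to change.** In Appendix 10.3, remove the upper limits so that each level is defined by its lower bound, with baseline at or below that bound:

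- ALT and AST: above 3, 5, 10 and 20 x ULN.
- Total bilirubin: above 1.5 and 2 x ULN.
- CPK: above 3 and 10 x ULN.

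State in words that the lowest open-ended level is the required one. Replace both counting comments with one rule for all four rows: a patient is counted at every level whose criterion is met.

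Showing the higher levels as well remains useful. A patient whose baseline already exceeds the lowest bound cannot qualify at that level, and a rise from there can show only at a higher one.

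The cost is a short edit to the appendix and the table program, using data already collected. Counts at the lowest level may come out slightly higher than under the closed bands.

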#### 10.4. Search Criteria for TEAE of Special Interest/TEAE Syndrome

| AESI  | Search Criteria  |
|---|--|
| Anaphylactic reactions  | Narrow SMQ for “anaphylactic reaction”   |
| Acute allergic reactions that require treatment   | 
 
Narrow SMQ for “hypersensitivity”
 
TEAE occurred due to the medication taken and recoded on ConMed CRF page
 
 
Note: Blinded manual adjudication of relevant PTs will be required by the study medical monitor, before database locks
 |
| Severe ISRs that last longer than 24 hours  | 
 
-HLT = Injection site reactions
 
- Severity = “severe”
 
   |
| Mycosis fungoides or other forms of cutaneous T cell lymphoma   | 
 
-HLT = “Mycosis fungoides”
 
Includes LLT = Sezary syndrome
 
Includes LLT = Cutaneous T-cell lymphoma
 
 
 
-PT = “Cutaneous T-cell dyscrasia”
 
  |
| Any severe infection  | 
 
-SOC = Infections and infestations
 
-Severity = “severe”
 
   |
| Any infection requiring treatment with parenteral antibiotics   | 
 
-SOC = Infection and infestations
 
-Action taken for AE = “medication”
 
- ConMed: ATC3= “Antiinfectives” during the TEAE course (between start and stop dates), Route = IV, IM
 
   |
| Any infection requiring treatment with oral antibiotic/anti-viral/anti-fungal for longer than 2 weeks | 
 
-SOC = Infection and infestations
 
-Action taken for AE = “medication”
 
-Check CM: ATC3= “Antiinfectives” during the TEAE course (between start and stop dates), Route = PO and Treatment duration >14 days
 
                           |
| Any clinical endoparasitosis  | 
 
-HLT = Cestode infections
 
-HLT = Helminthic infections NEC
 
-HLT = Nematode infections
 
-HLT = Trematode infection
 
  |
| Any opportunistic infection a  | 
 
The following HLTs plus PTs
 
-HLT = Pneumocystis infection
 
-HLT* = Fungal infections NEC
 
-HLT* = Pseudallescheria infections
 
-HLT = Herpes viral infections
 
-HLT = Paracoccidioides infections
 
               |

|                   |  |
|-------------------|--|
|                   | 

-HLT = Sporothrix infections

-HLT = Cryptosporidia infections

-HLT* = Trypanosomal infections

-HLT* = Campylobacter infections

-HLT* = Shigella infections

-HLT* = Vibrio infections

Plus the following PTs

-Polyomavirus-associated nephropathy

-BK virus infection

-Cytomegalovirus infection

-Post transplant lymphoproliferative disorder

-Progressive multifocal leukoencephalopathy

-*Bartonellosis

-Blastomycosis

-Toxoplasmosis

-Coccidioidomycosis

-Histoplasmosis

-*Aspergillus infection

-Systemic candida

-Oropharyngeal candidiasis

-Cryptococcosis

-Listeriosis

-Tuberculosis

-Nocardiosis

-Mycobacterial infection

-*Salmonellosis

-*Hepatitis B

-Herpes zoster

-*Strongyloidiasis

-Microsporidia infection

-Visceral leishmaniasis

-*Hepatitis C

 
Note: *Blinded manual adjudication of relevant PTs under each of HLTs listed above will be required by the study medical monitor, before database locks
 |
| Suicidal behavior | 
Include the following PTs
 

-Completed suicide

-Suicidal ideation

   |

a The definition of opportunistic infections is referring to the recent consensus guidance for opportunistic infections in the setting of biologic therapy ( K L Winthrop et al, 2015)

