#### Overall TEAE summary

The overall summary of TEAEs will be provided with number and proportions of patients with any:

- TEAE
- TEAE related to study drug
- Serious TEAE
- TEAE of special interest (AESI)
- TEAE leading to death

- TEAE leading to permanent treatment discontinuation

AESI

- Anaphylactic reactions
- Acute allergic reactions that require immediate treatment
- Severe injection site reactions that last longer than 24 hours
- Mycosis fungoides
- Cutaneous T-cell dyscrasia
- Any severe infection
- Any infection requiring treatment with parenteral antibiotics
- Any infection requiring treatment with oral antibiotics/anti-viral/anti-fungal for longer than 2 weeks
- Any clinical endoparasitisis
- Any opportunistic infection
- Suicidal behavior

[Appendix 10.5](#) provides a list of AESIs search criteria.

TEAE Incidence

Number and proportions of patients reporting TEAEs will be summarized for the following TEAEs:

- TEAEs
  - TEAEs by SOC/PT
  - TEAEs by SOC/HLT/PT
  - TEAEs by PT
  - TEAEs by SOC/HLT/PT with HLT  $\geq 5\%$  in any treatment groups
  - TEAEs by SOC/PT with PT  $\geq 5\%$  in any treatment groups
  - TEAEs by severity by SOC/PT
  - Severe TEAEs by SOC/PT
  - Severe TEAEs by SOC/HLT/PT
  - TEAEs related to study medication as assessed by the investigator by SOC/PT
  - Severe TEAEs related to study medication as assessed by the investigator by SOC/PT
  - TEAE of special interest/TEAE by category
- Serious TEAEs

- Serious TEAEs by SOC/PT
- Serious TEAEs by SOC/HLT/PT
- Serious TEAEs related to study medication as assessed by the investigator by SOC/PT
- TEAEs leading to permanent discontinuation of study treatment by SOC/PT
- Death by SOC/PT

Summary of the most frequent ( $\geq 5\%$ ) TEAEs by SOC, HLT, PT, respectively, in the dupilumab groups and in the overall study population will be provided.

SAEs/AESI during the Week 12 treatment period, follow-up period, and overall period will be listed.

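### Two AESI searches in SAP Appendix 10.4 do not match their labels: suicidal behavior has no term for a non-fatal act, and the severe injection site reaction search has no 24-hour test

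*SAP*

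**What the plan says.** Section 5.8.1 (Overall TEAE summary) lists the AESI categories. One is "Severe injection site reactions that last longer than 24 hours"; another is suicidal behavior, which is named but not defined further. AESI is a line of the overall TEAE summary, and the incidence tables include "TEAE of special interest/TEAE by category".

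Appendix 10.4 turns each category into a search:

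- **Injection site row.** The label is "Severe ISRs that last longer than 24 hours". The criteria are "HLT = Injection site reactions" and severity recorded as severe. Nothing follows.
- **Suicidal behavior row.** The row opens with "Include the following PTs" and lists two: "Completed suicide" and "Suicidal ideation". It gives no SMQ, high level term or adjudication note.

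For the search criteria, section 5.8.1 sends the reader to Appendix 10.5, which is the EEsAI scoring algorithm. The criteria are in Appendix 10.4.

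**The concern.** An AESI table is read by its headings. If the search behind a heading selects different events, the count is wrong for that heading even when the program follows the SAP exactly.

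The two rows fail in different ways. The suicidal behavior search omits an event its label names, the non-fatal act, and admits one that is not behavior, ideation. The injection site search is only over-inclusive: a severe reaction lasting a few hours is reported under a heading that says it lasted more than 24. The omission is the more serious of the two.

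**Working it through.** No sample size, power or error rate enters this point. The check sets each label beside its search and asks whether any other text supplies what is missing.

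**1. Label against search**

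| Category | Label requires | Search selects | Mismatch |
|---|---|---|---|
| Injection site reaction | severe, and longer than 24 hours | HLT; severity | 0 of 2 criteria test duration |
| Suicidal behavior | a suicidal act, fatal or not | 2 preferred terms: one fatal act, one thought | 0 of 2 terms retrieve a non-fatal act; 1 of 2 is not an act |

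**2. Does the table normally code durations?** Yes. The oral anti-infective row also has a duration in its label, and its search tests it: "Route = PO and Treatment duration" of more than 14 days. Leaving out the 24-hour test is therefore not a convention of the table.

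**3. Does adjudication repair either row?** No. Blinded manual review is specified in the acute allergic reaction row and for the starred terms of the opportunistic infection row. Neither row at issue carries a star or a note.

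**4. Result of following the plan**

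- Non-fatal attempt only: adds 0 to suicidal behavior.
- Ideation only: adds 1 to suicidal behavior.
- Severe injection site reaction of a few hours: adds 1 under a heading of more than 24 hours.

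**5. Can duration be tested with the data described?** Section 6.3 shows that AE start and end dates are collected. Section 5.8.1 names start date, end date and duration as variables for the listings of SAEs, deaths and discontinuations. Section 6.1 uses AE time as well as date for baseline, but the SAP mentions no end time, so a date-only rule is needed as a fallback.

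Let d = recorded end date − recorded start date, in days. The true duration lies between 24(d − 1) and 24(d + 1) hours, with a floor of 0:

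- d = 0: under 24 hours, so not a qualifying event.
- d = 1: above 0 and under 48 hours, so undetermined.
- d = 2: above 24 and under 72 hours, so confirmed. Larger d is also confirmed.
- Still ongoing at a contact 2 or more days after the start: above 24 hours, so confirmed.

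**6. Why imputed start dates should not feed this test.** Section 6.3 says AE start dates are used for the AESI analysis and imputes incomplete ones. For an event after the first dose, its rules give an early date: the first-dose date, the first of the month or 1 January. That lengthens the apparent duration. Example: start day missing, in a month after the first-dose month, end recorded as the 20th. The start becomes the 1st and d = 20 − 1 = 19, a confirmed event, even if the reaction began on the 20th. The fallback to the AE end date applies only when the event ended before the first dose, so it does not concern reactions to study drug. Imputed end dates are an intermediate step in 6.3 and are not kept in the final dataset.

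**The case against.** The strongest objection concerns the suicidal behavior row. Section 5.8.1 names the category without defining it, so the mismatch is with the ordinary meaning of the label and not with an explicit definition. The words "Include the following PTs" could also be read as an open list. Both observations are fair. However, the SAP gives no further term or rule, so a programmed search can use only the two terms shown. If the list is open, the choice of terms is left unspecified. No natural reading of the label takes in ideation and completed suicide but leaves out an attempt.

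The protocol, which is not at hand, might provide an investigator's AESI flag. The SAP refers to none for these rows, and Appendix 10.4 sets its own search.

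The effect is small, and this stands in full. Section 10.1 lists adverse events as descriptive, AESIs are also listed individually, an attempt reported as a TEAE remains visible by preferred term, and no qualifying injection site reaction is lost.

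A date rule with confirmed and unconfirmed counts may look heavy for one missing criterion, and it keeps some undetermined events in the category. The alternatives are to drop undetermined events, which could lose true ones, or to remove the 24-hour condition from both the label and section 5.8.1. One part of this objection should be taken up: an exception to the imputation rule must be visible in section 6.3 as well as in Appendix 10.4.

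**Conclusion.** The concern holds, as a minor point. The 24-hour mismatch is explicit: section 5.8.1 and the row label both state the condition, and the search omits it. The suicidal behavior mismatch rests on the plain meaning of the label and on the search using only the terms listed.

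Followed as written, the SAP puts wrong counts under two AESI headings whenever such events occur. It gives no expected rate for either event, so no effect on the reported percentages is claimed, and there is none if no such event occurs. No efficacy result is touched. The wrong appendix number in 5.8.1 is clerical.

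**What to change.** Before database lock:

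1. **Suicidal behavior row, Appendix 10.4.** Add the preferred terms for non-fatal suicidal acts (attempt, and self-injury with suicidal intent), with names taken from MedDRA 19.1, the version set in section 4.5.1. Show ideation on its own line, or relabel the row to cover both ideation and behavior.
2. **Severe injection site reaction row, Appendix 10.4.** Add a duration criterion. Use recorded start and end times if collected, otherwise recorded, non-imputed dates:
   - same-day start and end: not counted;
   - end 2 or more days after start, or ongoing at a visit or contact 2 or more days after start: counted as confirmed;
   - 1-day difference, or a partial or missing start or end date: counted and flagged as duration not confirmed.

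   Report confirmed and unconfirmed numbers separately. State in the row that start dates imputed under section 6.3 are not used for this test, and note the exception in 6.3.
3. **Section 5.8.1.** Change the pointer for the search criteria from Appendix 10.5 to Appendix 10.4.

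The cost is an edit to two rows of one table, one cross-reference, a sentence in 6.3 and the search program. The date-only rule uses AE dates already collected.
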